3.6 Post Study Drug Study Follow up

PFS and OS are key endpoints of the study. Post treatment study follow-up is essential to preserving subject safety and the integrity of the study. Subjects who discontinue study treatment prior to progression must continue to be followed for collection of protocol-defined PFS. Subjects who discontinue study therapy must also continue to be followed for overall survival data until death or the conclusion of the study.

BMS may request that survival data be collected on all randomized subjects outside of the protocol defined window, [Table 5.1-3](#).

At the time of this request, each subject will be contacted to determine their survival status unless the subject has withdrawn consent for all contact.

4 TREATMENTS

All protocol-specified investigational and noninvestigational products are considered study drug.

4.1 Study Treatments

Table 4.1-1: Product Description: Treatment Period					
Product Description and Dosage Form	Potency	Primary Packaging (Volume)/ Label Type	Secondary Packaging (Qty)/Label Type	Appearance	Storage Conditions (per label)
Elotuzumab Powder for Solution for Infusion	400 mg/vial	20 mL Vial/ Open Label	TBD	Sterile, white to off-white, preservative-free, lyophilized cake	Store at 2 °C - 8 °C Protect from light. Do not freeze or shake.
Lenalidomide (Revlimid [®]) capsule	5 mg, 10 mg, 15 mg and 25 mg	21 capsules per bottle OR blisters containing 7 capsules each/ Commercial or Open Label	NA/wallet or carton containing 21 capsules/ Commercial or Open Label	5 mg hard white capsule with "5 mg REV" written on them 10 mg hard yellow/blue-green capsule with "10 mg REV" written on them 15 mg hard white/blue capsule with "15 mg REV" written on them 25 mg: hard white capsule with "25 mg REV" written on them	Store at 25 °C (77 ° F). Excursions permitted to 15 - 30 °C (59 - 86 °F)
Dexamethasone Tablets	2 mg and 4 mg & various strengths	Various packing configurations	NA	Various	Refer to label on container or package insert/summary of product characteristics
Dexamethasone Solution	4 mg/ml, 8 mg/ml & various strengths	Various packing configurations	NA	Various	Refer to label on container or package insert/summary of product characteristics

Lenalidomide (Revlimid[®]) capsules, dexamethasone tablets and solution for IV infusion will be obtained by the investigating site's standard prescribing procedures. Lenalidomide (Revlimid[®]) may be supplied by BMS according to country availability and specific regulatory requirements.

4.1.1 Investigational Product

An investigational product, also known as investigational medicinal product in some regions, is defined as follows:

A pharmaceutical form of an active substance or placebo being tested or used as a reference in a clinical study, including products already with a marketing authorization but used or assembled (formulated or packaged) in a way different from the authorized form, or used for an unauthorized indication, or when used to gain further information about the authorized form.

The investigational product should be stored in a secure area according to local regulations. It is the responsibility of the investigator to ensure that investigational product is only dispensed to study subjects. The investigational product must be dispensed only from official study sites by authorized personnel according to local regulations.

In this protocol, investigational product(s) is/are: Elotuzumab powder for solution for infusion, lenalidomide (Revlimid[®]) capsules 5 mg, 10 mg, 15 mg, and 25 mg, dexamethasone tablets and concentrate for solution for IV infusion.

4.1.2 Noninvestigational Product

Other medications used as support or escape medication for preventative, diagnostic, or therapeutic reasons, as components of the standard of care for a given diagnosis, may be considered as noninvestigational products.

In this protocol, non-investigational product(s) are: diphenhydramine (or equivalent H1 blocker), ranitidine (or equivalent H2 blocker), acetaminophen, warfarin, low-molecular weight heparin and aspirin.

4.1.3 Handling and Dispensing

The product storage manager should ensure that the study drug is stored in accordance with the environmental conditions (temperature, light, and humidity) as determined by the Sponsor. If concerns regarding the quality or appearance of the study drug arise, do not dispense the study drug and contact the Sponsor immediately.

The investigator (or assigned designee, ie, study pharmacist) will dispense the proper number of each strength tablet to the subject to satisfy dosing requirements until the subject's next visit. The subject must be instructed to return all unused study medications in the provided packaging at each subsequent visit.

Procedures for proper handling and disposal of anticancer drugs should be considered.

4.1.3.1 Elotuzumab

The lyophilized elotuzumab drug product should be stored at 2° to 8°C. Prior to administration the drug product must be reconstituted with Sterile Water for Injection, USP, and then further diluted in 0.9% sodium chloride normal saline, USP, as per the instructions in [Appendix 6](#). After the dose is diluted in normal saline, the elotuzumab infusion must be administered within 8 hours if stored at room temperature. If a delay is anticipated, the prepared dose may be refrigerated at

2° to 8°C for up to 24 hours. If stored under refrigerated conditions, the prepared study drug solution should be equilibrated to room temperature (process takes 2 - 2.5 hours) and the container must be gently inverted to mix well before administration. Do not use the accelerated warming method. If administration is delayed beyond the specified time, the prepared dose solution must be discarded, and the reason documented by the pharmacist in study drug accountability records. The dose of elotuzumab to be administered to a subject will be calculated by multiplying the subject's weight (kg) by 10 mg/kg (20 mg/kg for Cycle 19 and beyond). The subject's predose weight on Day 1 of each cycle will be used to calculate the dose for each cycle. Subjects will receive a dose of elotuzumab IV on Days 1, 8, 15, and 22 of the first 2 cycles and on Days 1 and 15 of subsequent cycles (day 1 only for Cycle 19 and beyond). Each dose should be infused as per instructions in [Appendix 6](#).

4.1.3.2 Lenalidomide

Lenalidomide is an analogue of thalidomide. Thalidomide is a known human teratogen that causes severe life-threatening human birth defects. If lenalidomide is taken during pregnancy, it may cause birth defects or death to an unborn baby. Females should be advised to avoid pregnancy while taking lenalidomide (Revlimid[®]) and for up to 8 weeks after the last dose of lenalidomide. Furthermore, subjects taking lenalidomide should refrain from donating blood until at least 8 weeks or sperm until at least 90 days after last dose of lenalidomide.

Because of this potential toxicity and to avoid fetal exposure to lenalidomide, lenalidomide is only available under a special restricted distribution program.⁴² This program is called the Revlimid Risk Management Plan. Under this program, only prescribers and pharmacists registered with the program can prescribe and dispense the product. In addition, lenalidomide must only be dispensed to subjects who are registered and meet all the conditions of the Revlimid Risk Management Plan. Subjects who have the potential of pregnancy in the Revlimid Risk Management Plan must be instructed about contraception and undergo the scheduled pregnancy tests.

Please see the US package insert/SMPC⁴⁸ for additional information for prescribing to, female subjects and male subjects about this restricted distribution program.

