3.3.1 Inclusion Criteria

1. Signed Written Informed Consent

- a) Subject is, in the investigator's opinion, willing and able to comply with the protocol requirements.
- b) Subject has given voluntary written informed consent before performance of any study-related procedure not part of normal medical care, with the understanding that consent may be withdrawn by the subject at any time without prejudice to their future medical care.

2. Target Population

- a) Age \geq 18 years or legal age of consent per local regulations.
- b) ECOG performance status \leq 2.
- c) Life-expectancy $>$ 3 months.
- d) Newly diagnosed, untreated, symptomatic, documented myeloma AND;
 - i) Who are not candidates for high-dose therapy plus SCT because of age (\geq 65 years) or coexisting conditions. Refusal to undergo high dose therapy with SCT is **NOT** sufficient for entry onto CA204006 for a subject $<$ 65 years old. There must be a comorbidity that prevents SCT for a subject $<$ 65 years old, AND;
 - ii) Measureable disease (patient must meet one of these criteria)
 - (a) serum IgG M-protein \geq 0.5 g/dL OR
 - (b) serum IgA M-protein \geq 0.5 g/dL OR
 - (c) serum IgM M-protein \geq 0.5 g/dL OR
 - (d) serum IgD M-protein \geq 0.05 g/dL OR
 - (e) Urine M-protein \geq 200 mg/24-hour

3. Age and Reproductive Status

- a) Women of childbearing potential (WOCBP) and men must be using 2 acceptable methods of contraception to avoid pregnancy throughout the study for a period of at least 1 month (4 weeks) before and women for up to 120 days, men for up to 180 days after the last dose of investigational product in such a manner that the risk of pregnancy is minimized. See [Section 3.3.3](#) for the definition of WOCBP and also refer to the Revlimid risk management plan guidelines.
- b) WOCBP must have a negative serum or urine pregnancy test (minimum sensitivity 25 IU/L or equivalent units of HCG). The first should be performed within 10 - 14 days and the second within 24 hours prior to the start of the investigational product. A prescription for lenalidomide for a female of childbearing potential must not be issued by the prescriber until negative pregnancy tests have been verified by the prescriber.
- c) Women must not be breastfeeding.
- d) Women who are not of childbearing potential (ie, who are postmenopausal or surgically sterile; see Section 3.3.3 for the definition of WOCBP) and men.

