- e) Sexually active fertile men must use effective birth control if their partners are WOCBP. Men must agree to use a latex condom and a second form of birth control during sexual contact with WOCBP, even if they have had a successful vasectomy, and must agree to not donate semen during study drug therapy and for 180 days after therapy.
- f) Subjects must be willing to refrain from blood donations during study drug therapy and for 90 days after therapy.

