Performance Status (ECOG)	X					X			Evaluate prior to dosing
Serious Adverse Event Assessment	X		X*			X	X		Evaluate prior to dosing *Not required in Cycles 19 and beyond
Adverse Events Assessment	X		X*			X	X		Evaluate prior to dosing *Not required in Cycles 19 and beyond
Second Primary Malignancy	X		X			X	X	X	Section 6.7: Performed at 30 and 60 day \pm 1 week EOT follow up visits. After 30 and 60 day EOT visits, second primary malignancy should be assessed every 16 weeks (\pm 2 weeks), or more frequently. Subjects should be followed monthly (if no Progression) or every 16 weeks (if Progression occurred), or more frequently.
Concomitant Medications	X		X*			X	X		Evaluate prior to dosing

Table 5.1-3: Long-term Procedural Outline (CA204006) Cycles 3 and Beyond									
Procedure	Day 1	Day 8	Day 15	Day 22	Rest Days 23 - 28	End of Treatment	Days 30 & 60 Post End of Treatment	Every 16 weeks after progression	Notes
Subsequent Myeloma Therapy						X	X	X	30 and 60 day visits may be performed ± 1 week. After 30 and 60 day EOT visits and EBMT based progression subsequent myeloma should be assessed every 16 weeks (± 2 weeks), or more frequently. Subjects should be followed monthly (if no Progression) or every 16 weeks (if Progression occurred), or more frequently. Start date and end date for second and third line therapy and date of progression after second line therapy will be collected.
Laboratory Tests for Safety									
CBC, differential, platelets	X		X*			X			Section 5.3.4 Can be drawn up to 3 days prior to visit. *Not required in Cycles 19 and beyond
Serum Chemistry	X		X*			X			Section 5.3.4 Can be drawn up to 3 days prior to visit *Not required in Cycles 19 and beyond
Coagulation Tests	X		X*			X			For subjects treated with warfarin thromboembolic prophylaxis *Not required in Cycles 19 and beyond

Table 5.1-3: Long-term Procedural Outline (CA204006) Cycles 3 and Beyond									
Procedure	Day 1	Day 8	Day 15	Day 22	Rest Days 23 - 28	End of Treatment	Days 30 & 60 Post End of Treatment	Every 16 weeks after progression	Notes
Pregnancy Test	X		X*			X	X**		For WOCBP only. Urine tests must have a sensitivity of at least 25 IU/L. Test must be completed on Day 1 and Day 15 within 24 hours prior to dosing. * Not required in Cycles 19 and beyond. However, patients with irregular menstrual cycles must have a pregnancy test every two weeks. ** WOCBP must have a pregnancy test 30, 60, and 90 days Post End of Treatment.

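### Section 4.1.3.2 advises women to avoid pregnancy for up to 8 weeks after lenalidomide, 64 days short of the 120 days in inclusion criterion 3(a), and does not refer to that criterion

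*Protocol*

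**What the plan says.** Three places in the Protocol bear on how long a woman should avoid pregnancy after treatment.

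- **Section 4.1.3.2 (Lenalidomide)** describes the drug as an analogue of a known human teratogen. It says females should be advised to avoid pregnancy during lenalidomide and "for up to 8 weeks after the last dose of lenalidomide". For more detail it sends the reader to the Revlimid Risk Management Plan and the package insert/SMPC. It does not mention section 3.3.1.
- **Section 3.3.1, criterion 3(a)** says that women of childbearing potential and men "must be using 2 acceptable methods of contraception to avoid pregnancy throughout the study", and it extends the duty to "women for up to 120 days, men for up to 180 days after the last dose of investigational product". It adds that readers should "also refer to the Revlimid risk management plan guidelines", without saying which period prevails if the two differ.
- **Section 4.1.1** settles what the 120 days run from: "In this protocol, investigational product(s) is/are: Elotuzumab powder for solution for infusion, lenalidomide", with dexamethasone also on the list. Criterion 3(a) is not restricted to one arm, so the 120 days apply after lenalidomide in both arms.

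Section 6.4 uses the same 120 days as the window for reporting a pregnancy exposure. Table 5.1-3 in section 5.1 continues testing after treatment: "WOCBP must have a pregnancy test 30, 60, and 90 days Post End of Treatment".

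**The concern.** Section 4.1.3.2 is the place where site staff look up what to tell a woman about lenalidomide and pregnancy. It gives an end point for that advice, and the end point comes earlier than the protocol's own requirement. Nothing in the section warns that a longer period applies in this trial. Its only onward references are to the lenalidomide distribution programme and labelling.

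What is at stake is counselling at the end of treatment. By then eligibility was checked months or years ago, and staff may well turn to the drug-specific section. A woman advised from that section alone could stop contraception at week 8 and would then be outside criterion 3(a). The hazard is fetal exposure. The trial's efficacy and safety analyses are not touched.

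**Working it through.** **Inputs**

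| Quantity | Value | Source (Protocol) |
|---|---|---|
| Advised pregnancy avoidance after lenalidomide | up to 8 weeks | 4.1.3.2 |
| Required contraception, women, after investigational product | up to 120 days | 3.3.1, criterion 3(a) |
| Lenalidomide is an investigational product | yes | 4.1.1 |
| Washout; ovulatory cycle | 90 days; 30 days | 6.4 |
| Post-treatment pregnancy tests | days 30, 60, 90 | Table 5.1-3 |
| Window on the 30- and 60-day visits | ±1 week | Table 5.1-3, notes to other rows |

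**Step 1. Reproduce the protocol's figure.** Section 6.4 builds its window as washout plus one ovulatory cycle: 90 + 30 = 120 days. This agrees with criterion 3(a). Section 6.4 concerns exposure reporting, so it corroborates the 120 days; the contraception duty itself comes from criterion 3(a).

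**Step 2. Put the advice in days.** 8 × 7 = 56 days.

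**Step 3. Compare, all drugs stopped on the same day.** Shortfall: 120 − 56 = 64 days. Share of the required period covered: 56 / 120 = 46.7%. Both texts say up to, so each is read here as its full stated length.

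**Step 4. Lenalidomide stopped first.** If another investigational product continues for k days after the last lenalidomide dose, criterion 3(a) ends 120 + k days after that dose, and the difference is 120 + k − 56 = 64 + k days. Since k cannot be negative, 64 days is the smallest difference. While treatment continues, the woman is covered by the requirement in criterion 3(a) to use contraception throughout the study.

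**Step 5. Compare with the testing schedule.** Take End of Treatment as the day of the last lenalidomide dose. The day-30 test falls inside the 56 days. The day-60 test is nominally 60 − 56 = 4 days later, but if it is done at the 60-day visit with its ±1 week window it could fall on day 60 − 7 = 53, inside the 56 days. The pregnancy-test row states no window of its own. The day-90 test is 90 − 56 = 34 days later, and would still be later if a week were taken off (90 − 7 = 83). So only the day-90 test clearly shows monitoring beyond week 8.

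**The case against.** The strongest reply is that the protocol already shows which text binds. Section 3.3 makes the entry criteria mandatory, and section 3.3.2 closes by insisting that they be met in full. Criterion 3(a) is a requirement, whereas section 4.1.3.2 is advice. No woman of childbearing potential can enter without accepting 120 days. Section 4.1.3.2 sits under handling and dispensing, speaks of one drug, and starts its clock at the last dose of that drug. The Amendment 06 entry in the document history ties the contraception update to elotuzumab pharmacokinetic data, which would explain why the lenalidomide paragraph has a different figure. On this view only a cross-reference is missing.

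Most of this stands. Criterion 3(a) governs, following it satisfies both texts, and the 8 weeks is specific to lenalidomide. It does not remove the point. Criterion 3(a) is not limited to the elotuzumab arm, and section 4.1.1 starts its clock at lenalidomide too. Within this trial, advice that ends at 56 days is therefore short of what is required, whatever the origin of the 8 weeks.

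A reader might go further in several ways that the documents do not support:

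- **That the sections contradict each other.** They do not; the longer period contains the shorter.
- **That the day-60 and day-90 tests both fall after the advice ends.** The visit window leaves this certain only for day 90.
- **That the donation periods in the same paragraph are also wrong.** Section 4.1.3.2 says subjects "should refrain from donating blood until at least 8 weeks or sperm until at least 90 days after last dose of lenalidomide". Section 3.3.1 says men "must agree to not donate semen during study drug therapy and for 180 days after therapy" and sets 90 days for blood. The figures in section 4.1.3.2 are worded as minimums, so they are compatible with the longer periods and are not evidence of error.
- **That a woman who stops lenalidomide but continues elotuzumab is left uncovered.** The throughout-the-study wording in criterion 3(a) covers her.
- **That women were given wrong advice, or that 8 weeks is wrong for lenalidomide itself.** The consent pages and the labelling are not available here, so neither can be judged.

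**Conclusion.** The point holds as a minor error in safety wording. An instruction on counselling about a teratogen gives an end point at least 64 days earlier than the protocol's own requirement, covering 47% of the required period when all drugs stop together, and does not direct the reader to the section that governs.

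The practical risk is low. Every woman of childbearing potential enters under criterion 3(a). Few such women are expected, because subjects are ineligible for transplantation through age of 65 years or more or through coexisting conditions. The number is not necessarily zero: the lower age limit is 18 years or the local age of consent, subjects under 65 can qualify through comorbidity, and the protocol has a full pregnancy-testing schedule for them. There is no effect on endpoints, power, error rates or analysis.

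The conclusion assumes that both periods are read at their full stated length and that section 4.1.1 defines investigational product wherever section 3.3.1 uses the term.

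**What to change.** Amend section 4.1.3.2 so that females are advised to avoid pregnancy during treatment and for 120 days after the last dose of any investigational product, as section 3.3.1 requires. If the lenalidomide-specific 8 weeks is kept for reference, state beside it that section 3.3.1 governs in this trial. For consistency, the same sentence can point to the donation periods in section 3.3.1 (180 days for semen and 90 days for blood). Check that the consent form gives the same periods.

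The cost is one sentence in an amendment and a document check. No procedure, data collection or analysis changes.

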4.2 Method of Assigning Subject Identification

After the subject's eligibility is established and informed consent has been obtained, the subject must be enrolled into the study by calling an interactive voice response system (IVRS) to obtain the subject number. The following information is required for subject enrollment:

- Date of Birth
- Site number
- Date that informed consent was obtained

Instructions on the use of interactive voice response system will be provided at site initiation.

When it has been determined that a subject is eligible for randomization, a call will be placed to IVRS to obtain treatment assignment. Subjects will be randomized to lenalidomide/dexamethasone + elotuzumab (Arm A) or lenalidomide/dexamethasone alone (Arm B) in a 1:1 ratio. The randomization will be stratified by the following factors:

- Stage of Disease (International Staging System 1 - 2 versus 3)
- Age (< 75 years old versus ≥ 75 years old)
- ECOG Performance Status (0 versus 1 - 2)

and will be carried out via permuted blocks within each stratum.

4.3 Selection and Timing of Dose for Each Subject

4.3.1 Study Drug Administration

Dexamethasone

On weeks without elotuzumab (including the control arm), administer the weekly dose of 40 mg dexamethasone on Day 1, 8, 15, and 22 (-1 to +3 days). At the investigator's discretion, the oral dexamethasone may be given as a split dose over 2 consecutive days each week.

On weeks of elotuzumab infusion, administer dexamethasone as a split dose of:

- 28 mg po (between 3 - 24 hours prior to the start of elotuzumab infusion) AND
- 8 mg IV (on the day of elotuzumab infusion at least 45 min prior to the start of infusion).
- At the discretion of the investigator, the oral dexamethasone component may be given as a split dose 12 - 24 and 3 hours prior to elotuzumab.

Elotuzumab

Elotuzumab will be administered intravenously at a dose of 10 mg/kg weekly (Days 1, 8, 15, and 22 of a 4-week cycle) of the first 2 cycles and every 2 weeks (Day 1 and Day 15) for cycles 3 through 18, then at a dose of 20 mg/kg every 4 weeks Cycle 19 (Day 1) and beyond. A window of -1 to + 3 days is permitted in Cycles 1 and 2.

In Cycle 1 and 2, an elotuzumab dose that falls outside of the pre-specified window must be skipped.

In Cycles 3 and beyond, elotuzumab dosing may be delayed for up to 1 week as clinically indicated. The reason for the delay must be recorded on the CRF. If unable to administer within 1 week, then the dose should be skipped and resumption of the elotuzumab continues per the protocol defined schedule.

In addition, the following must also be administered 30 - 90 min prior to any elotuzumab:

- H1 blocker: diphenhydramine (25 - 50 mg po or IV) or equivalent;
- H2 blocker: ranitidine (50 mg IV) or equivalent
- acetaminophen (650 - 1000 mg po)

See [Appendix 6](#) for elotuzumab dosing instructions.

Lenalidomide

Lenalidomide will be taken orally once daily for the first 3 weeks of a 4-week cycle. Subjects should not break, chew or open the capsules.

Table 4.3.1-1: Treatment Schedule												
Control Arm												
Cycle #	1 - 2				3 - 18				19+			
Day # (-1/+3 days)	1	8	15	22	1	8	15	22	1	8	15	22
Lenalidomide - PO	←25 mg Days 1 - 21→				←25 mg Days 1 - 21→				←25 mg Days 1 - 21→			
Dexamethasone - PO	40 mg	40 mg	40 mg	40 mg	40 mg	40 mg	40 mg	40 mg	40 mg	40 mg	40 mg	40 mg
Investigational Arm												
Cycle #	1 - 2				3 - 18				19+			
Day # (-1/+3 days)	1	8	15	22	1	8	15	22	1	8	15	22
Lenalidomide - PO	←25 mg Days 1 - 21→				←25 mg Days 1 - 21→				←25 mg Days 1 - 21→			
Dexamethasone - PO	28 mg	28 mg	28 mg	28 mg	28 mg	40 mg	28 mg	40 mg	28 mg	40 mg	40 mg	40 mg
Dexamethasone - IV	8 mg	8 mg	8 mg	8 mg	8 mg	-	8 mg	-	8 mg	-	-	-
Elotuzumab - IV	10 mg/kg	10 mg/kg	10 mg/kg	10 mg/kg	10 mg/kg	-	10 mg/kg	-	20 mg/kg	-	-	-

